Other possible adverse reactions may include lactic-acidosis, fungal peritonitis, peritonitis bacterial, catheter-related infections, hypovolemia, hypervolemia, fluid retention, hypokalemia, hyponatremia, dehydration, hypochloremia, hypotension, hypertension, dyspnea, peritonitis, peritoneal cloudy effluent, vomiting, diarrhea, nausea, constipation, abdominal pain, abdominal distension, abdominal discomfort, Stevens-Johnson syndrome, urticaria, rash (including pruritic, erythematous and generalized), pruritus, myalgia, muscle spasms, musculoskeletal pain, generalized edema, pyrexia, malaise, infusion site pain, and catheter related complication.

Potential benefits for these subjects include earlier closure, fewer ventilator days, earlier feeding and decreased length of stay.

There will be no direct benefits to the study participants in the SoC group; however, knowledge gained from the study could potentially benefit subjects in the future as it guides us in best practices for pediatric patients with gastroschisis.

Subject Withdrawal from Study

Subjects' parent(s)/LAR may choose to withdraw from the study for any reason. Additionally, the investigator may choose to remove subjects from the study. This may occur for the following reasons:

- Serious adverse event believed to be related to investigational product
- Intolerable side effects
- Clinically significant laboratory abnormalities
- The investigator believes it is in the best interest of the subject to discontinue the study

Any subject withdrawing their consent to participate in the study or their authorization to use their protected health information will be withdrawn from the study. Neonates who are withdrawn from the study will no longer undergo any study-related procedures or data collection. Standard of care treatment will be continued.

Reasons why subjects are discontinued from the clinical trial will be documented on the Study Termination Form.

Safety Monitoring

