Given the risk for fluid and electrolyte imbalances, close monitoring will be provided for the DPR group by using more frequent clinical and laboratory assessments in addition to standard NICU monitoring. Vital signs and strict intake and output will be monitored every 6 hrs for 48 hours after maximum dialysate infusion volume (100 mL) is reached, then every 12 hrs (\pm 30 minutes). Sodium, potassium, blood glucose and lactate levels will be monitored every 6 hours (\pm 30 minutes) via heelstick, central/arterial line or venipuncture per NICU standard practice for 24 hours after the maximum dialysate infusion volume is reached, then every 12 hrs (\pm 30 minutes) through Post-Closure Day 1.

Title: Direct Peritoneal Resuscitation in Gastroschisis

PI: [name]

Sponsor: UAMS

Subject will also be monitored for the following potential adverse events:

1. Hypokalemia: If the potassium falls to <3.0, additional potassium will be added to the IV fluid at the discretion of the treating and study physicians.
2. Lactic acidosis: Lactate levels will be monitored with laboratory checks at least every 12 hours during the treatment phase. Continued monitoring of lactic acidosis will include laboratory checks, fluid replacement, and stopping infusion of the dialysate fluid.
3. Hyperglycemia: During the first day (24 hrs) of treatment, blood glucose will be obtained within 1 hour prior to infusion and 1 hour (\pm 15 minutes) post-infusion in addition to routine daily assessments. The neonatologists will change IVFs to contain less dextrose as needed.
4. Hypovolemia: This will be treated with fluid replacement. Blood pressure monitoring and urine output assessment will guide management for amount of fluid replacement needed.
5. Peritonitis: This will be evaluated daily by examination of the effluent dialysate for any cloudiness. Cloudy fluid will be sent to the laboratory for cell count, gram stain, and culture. If the cell count is elevated, the subject will receive antibiotics as indicated. Subjects with confirmed peritonitis will be withdrawn from the study.
6. Definite (culture positive) sepsis: Neonates with active clinical sepsis will be excluded from the study by the hemodynamic parameter exclusion criteria (hypotension, hyper/hypoglycemia, lactic acidosis, etc.). During the dialysate infusion period, subjects who develop definite (culture positive) sepsis will be withdrawn from the study.

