7. Acute Kidney Injury (AKI): AKI will be staged using the “Neonatal AKI KDIGO Classification” Table below (Selewski *et al* [22]). Subjects who develop AKI > Stage 2 will be withdrawn from the study.

TABLE 1 Neonatal AKI KDIGO Classification

Stage	SCr	Urine Output
0	No change in SCr or rise <0.3 mg/dL	≥ 0.5 mL/kg/h
1	SCr rise ≥ 0.3 mg/dL within 48 h or SCr rise $\geq 1.5\text{--}1.9 \times$ reference SCr ^a within 7 d	<0.5 mL/kg/h for 6 to 12 h
2	SCr rise $\geq 2.0\text{--}2.9 \times$ reference SCr ^a	<0.5 mL/kg/h for ≥ 12 h
3	SCr rise $\geq 3 \times$ reference SCr ^a or SCr ≥ 2.5 mg/dL ^b or Receipt of dialysis	<0.3 mL/kg/h for ≥ 24 h or anuria for ≥ 12 h

Differences between the proposed neonatal AKI definition and KDIGO include the following:

^a Reference SCr will be defined as the lowest previous SCr value.

^b SCr value of 2.5 mg/dL represents <10 mL/min/1.73m².

Individual Subject Discontinuation

If a subject develops any of the individual subject discontinuation criteria below, the study drug will be immediately discontinued:

- Positive blood culture
- Documented peritonitis
- Lactic acid > 5 mmol/L
- pH < 7.1
- Sodium < 125 mEq/L or > 150 mEq/L
- Potassium < 2.5 mEq/L
- Continued hyperglycemia > 250 for more than 12 hours
- Definite (culture positive) sepsis
- Stage 3 AKI [22]

Title: Direct Peritoneal Resuscitation in Gastroschisis

PI: [name]

Sponsor: UAMS

Subjects who develop any of the individual subject discontinuation criteria will be evaluated and monitored until resolution of the adverse events and laboratory values have returned to baseline. These subjects will no longer receive DPR, but will continue with assessments per the schedule of procedures and assessments.

Study Discontinuation

The study will be stopped if more than 3 subjects in the DPR group develop any one of the individual subject discontinuation criterion above.

Adverse Events

For purposes of this study, the following will be considered adverse events of special interest if they occur before study completion:

1. Bradycardia: defined as a heart rate < 100 bpm for ≥ 20 seconds
2. Desaturation: defined as SpO₂ < 80% for ≥ 20 seconds
3. A sustained apnea event defined as lasting ≥ 20 seconds and coinciding with at least one of the following:
 - HR < 100 bpm
 - Desaturation (oxygen saturation < 80%)
4. Other AES of special interest have been adopted from England *et al.*'s adverse event tables for the Pediatric Trials Network (PTN) [23] (Appendix E).

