Demographic variables will be assessed for differences between groups. Categorical variables will be examined using Fisher's Exact Test or Chi Square Test. Continuous data will be examined using Students' T-test. All tests will be two-sided assuming a significance level of 5%. The dependent variable will be tested to ensure the assumption of normality is met.

The primary outcome measure is time to full enteral feeds of 100 kcal/kg/day. Using a two-sample t-test, we estimated that a sample size of 20 in each of the two groups will yield at least 80% power to detect a 6-day difference in mean time to goal enteral feeds (100 kcal/kg/day) assuming a common standard deviation of 7 and a two-sided significance level of 5%.

The proposed data analyses and sample size calculations were conducted with the support of statisticians at ACRI using SAS® Software, Version 9.4[24].

Ethical Considerations

This study is to be conducted according to applicable government regulations and Institutional research policies and procedures.

Title: Direct Peritoneal Resuscitation in Gastroschisis

PI: [name]

Sponsor: UAMS

The parent(s)/LAR of each potential subject identified as meeting inclusion criteria for this study will be approached to discuss participation in this study by trained study personnel. The person obtaining consent will go over the informed consent comprehensively with the parent(s)/LAR. The risks and rationale of this study will be outlined and all questions will be answered. The volunteer natures of this project will be emphasized, including uninhibited withdrawal from the study at any time. No coercion or undue influence will be used in the consent process. A copy of the signed consent will be given to the subject's parent(s)/LAR, and the informed consent process will be documented in each subject's research record in a separate process note.

Ways of consenting parent(s)/LAR:

1. Mother or father (if mother and father are married)/LAR consented prenatally in OB/GYN clinic.
2. Mother or father (if mother and father are married)/LAR consented after birth via faxed consent to the OB unit and returned to PI. The faxed consent will then be witnessed by bedside nurse.
 - a. The person obtaining consent will fax a consent form to the OB unit and conduct the consent process conversation by phone once the mother or father/LAR has the form in hand.

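### The withdrawal and discontinuation rules conflict on whether infants with peritonitis, sepsis or severe AKI keep a primary outcome, and losses would fall mainly in the DPR arm

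*Combined protocol and SAP*

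**What the plan says.** The primary outcome is time to enteral feeds of 100 kcal/kg/day. The Data Analysis section describes the test and size as follows: "Using a two-sample t-test, we estimated that a sample size of 20 in each of the two groups" gives at least 80% power for a 6-day difference with SD 7, two-sided 5%. It names no analysis set and gives no rule for an infant without a feeding date.

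Three sections deal with infants who have a serious problem during treatment.

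- **Safety Monitoring, items 5 to 7.** On peritonitis: "This will be evaluated daily by examination of the effluent dialysate for any cloudiness", and "Subjects with confirmed peritonitis will be withdrawn from the study". On sepsis: "During the dialysate infusion period, subjects who develop definite (culture positive) sepsis will be withdrawn from the study". On kidney injury: "Subjects who develop AKI > Stage 2 will be withdrawn from the study".
- **Subject Withdrawal from Study.** The investigator may remove an infant for reasons that include "Serious adverse event believed to be related to investigational product". The consequence of withdrawal is: "Neonates who are withdrawn from the study will no longer undergo any study-related procedures or data collection".
- **Individual Subject Discontinuation.** Documented peritonitis, culture-positive sepsis and Stage 3 AKI are on a list of reasons to stop study drug. Of infants who meet any of them it says: "These subjects will no longer receive DPR, but will continue with assessments per the schedule of procedures and assessments".

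**The concern.** The same three events lead to two different outcomes for the data. Under one set of sentences the infant leaves the study and nothing more is collected. Under the other, the infant only stops DPR and is followed as scheduled. With no analysis set defined, nothing else says whether such an infant contributes a time to full feeds.

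This matters because the routes to withdrawal do not bear equally on the two arms. Peritonitis is looked for in dialysate effluent, which control infants do not have. The sepsis rule is tied to the dialysate infusion period. A product-related serious event can arise only in infants who receive the product. If the infants who drop out are slower to feed than their peers, removing them makes the DPR arm look faster than it is. In a trial of 40, two or three infants are enough to matter.

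**Working it through.** **Step 1. The rules side by side.**

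| Event | Safety Monitoring | Individual Subject Discontinuation |
|---|---|---|
| Confirmed or documented peritonitis | withdrawn from study | DPR stops, assessments continue |
| Culture-positive sepsis | withdrawn (during infusion period) | DPR stops, assessments continue |
| AKI above Stage 2, i.e. Stage 3 in the three-stage table | withdrawn from study | DPR stops, assessments continue |

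The conflict is direct for these three events. The AKI rule and the other discretionary removal reasons (side effects, laboratory abnormalities, best interest) are not limited to one arm. Hence the loss would be mainly, not only, in the DPR arm.

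**Step 2. The plan's own figure.** Inputs from Data Analysis: n = 20 per arm, difference 6 days, SD 7, two-sided 5%. The standardized distance is 6 / (7 × √(2/20)) = 2.71. Normal-approximation power is Φ(2.71 − 1.96) = 77.4%, and the exact (noncentral t) power is 75.2%. The stated 80% is not reproduced. That is a separate matter, but it means there is no reserve for lost dates. If 1, 2 or 3 DPR dates are lost at random, exact power falls to 74.1%, 72.8% or 71.4%.

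**Step 3. Bias if the lost infants are slower.** The documents give no loss rate, so the counts are assumptions. One to three is a reasonable range to show: under Study Discontinuation the trial stops only when more than 3 DPR infants meet any one criterion, so up to 3 of 20 (15%) per criterion can occur without stopping.

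Take normal data, SD 7, no true effect, k DPR infants dropped and no controls dropped. The shift in the DPR mean is −7 × (sum of the standardized values of those dropped) / (20 − k).

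- Slower half: the average standardized value of the slower 10 of 20 is 0.767. The shift is 7 × 0.767 × k/(20 − k): 0.28 days (k = 1), 0.60 (k = 2), 0.95 (k = 3).
- Slowest: the expected top three standardized values of 20 are 1.87, 1.41 and 1.13. The shift is 7 × 1.87/19 = 0.69, 7 × 3.28/18 = 1.28 (1.27 unrounded) and 7 × 4.41/17 = 1.82 days (1.81 unrounded).

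**Step 4. Error of the t-test on the remaining infants** (simulation, 400,000 trials per row; nominal 2.5% in each direction, 5% in total).

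| Lost, DPR v SoC | Who is lost | False DPR benefit | False SoC benefit | Two-sided total |
|---|---|---|---|---|
| 1 v 0 | slower half | 3.2% | 1.8% | 5.0% |
| 2 v 0 | slower half | 4.2% | 1.2% | 5.4% |
| 3 v 0 | slower half | 5.5% | 0.8% | 6.3% |
| 1 v 0 | slowest | 5.4% | 1.4% | 6.8% |
| 2 v 0 | slowest | 9.3% | 0.8% | 10.1% |
| 3 v 0 | slowest | 14% | 0.4% | 14.5% |
| any of these | at random | 2.5% | 2.5% | 5.0% |

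The slowest rows are an upper bound. Smaller runs of 40,000 to 100,000 trials agree to within a few tenths of a point.

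**Step 5. What removes the bias.** If every infant stays in the assigned arm with its own date, no data are lost and the t-test is back at about 2.5% in each direction (2.4% and 2.5% in the simulation). No change of test is needed for this problem.

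**The case against.** The best reply is about reading. The sentence that ends data collection follows directly, in the same paragraph, a sentence about parents withdrawing consent or authorization, and can be read as covering only that case. Individual Subject Discontinuation speaks specifically to infants who meet the stopping criteria, and specific text can govern general text. On that reading nothing is lost. The reading is open, but it is not secured: the sentence is worded for all withdrawn neonates, the section also covers removals by the investigator, and Safety Monitoring uses the same term, withdrawal from the study, for these events. A study team could follow either.

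The second reply is about size, and much of it stands. In the slower-half case the two-sided error is only 5.0–6.3%, and the spurious gain is under a day against a 6-day target. Nothing in the documents shows that infants with peritonitis, sepsis or AKI would be the slowest feeders in their arm.

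A reader might also infer that the t-test must give way to a Wilcoxon test with worst ranks. The withdrawal problem does not support that, as step 5 shows. Worst ranks matter only for death or true failure to reach the goal, for which the documents give no rate, and they cost power: Wilcoxon power falls from 0.72–0.73 with complete data to about 0.53–0.63 if 10% per arm never reach the goal. Given automatically to infants merely lost at random, they would count against DPR (a false SoC benefit of 9.8% with 3 v 0).

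**Conclusion.** The point holds as an unresolved conflict over data capture, together with a missing analysis set. It is not a demonstrated bias. A reader might infer that the plan will discard treated infants with complications and so favour DPR. The documents do not support that, because one of the two conflicting sections keeps those infants under assessment, and because AKI and the discretionary removals can occur in either arm.

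If the withdrawal text is followed, the effect is modest to moderate: under the assumed losses of 1 to 3 DPR infants and no controls, a false DPR benefit of 3.2–5.5% in the slower-half case and at most about 14% in the extreme case. All of this rests on assumed loss counts, normal data with SD 7, and no true effect. It should be corrected because the remedy is cheap and the ambiguity sits on the primary outcome. The start of the clock for that outcome is also unstated. It should be given, but it is a separate detail.

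**What to change.** 1. Reconcile Subject Withdrawal from Study, Safety Monitoring items 5 to 7 and Individual Subject Discontinuation on data capture only. Unless consent or authorization is withdrawn, the date of reaching 100 kcal/kg/day should still be taken from the medical record after DPR stops. If the goal is reached after discharge, add that date to the existing chart review or phone call, which is now described for durability and adverse events. This does not touch when DPR stops.
2. State the analysis set: all eligible randomized infants, by assigned arm, each on its own date. The Eligibility Criteria note allows infants found ineligible after randomization to be withdrawn and replaced, so apply that baseline check in the same way in both arms. With items 1 and 2 the planned t-test can stay.
3. Report by arm the number reaching the goal, the deaths, and the number with no date and why. Deaths, short gut and transplant transfer are collected items, so some infants may truly have no date. Add a rank-based sensitivity analysis: worst rank for death or known failure to reach the goal, and both best and worst rank where status is unknown.

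The cost is a text edit, one added follow-up item, and a little more chart abstraction and analysis. The Data to be obtained section says that the feeding items are already in the infants' records, so no new clinical procedure is involved.

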The investigational product will be kept in a secure, limited-access storage in the ACRI research pharmacy under the direction of the research pharmacists who will be responsible for maintaining the supply according to the manufacturer's specifications, dispensing the drug for administration, and maintaining all drug accountability logs.

Study Population

We will prospectively enroll all neonates with the diagnosis of gastroschisis presenting to ACH within 12 hours after birth for whom consent is signed by the parent(s)/LAR. We anticipate enrolling 40 subjects at Arkansas Children's Hospital. All subjects that have their abdominal wall defect closed will be defined as having completed active participation in the study.

Eligibility Criteria

Inclusion criteria:

- Diagnosis of Gastroschisis
- Male or Female, any ethnicity
- Neonates [18]

Exclusion criteria:

- Primary gastroschisis repair
- Vanishing gastroschisis
- Encapsulating peritoneal sclerosis
- Infants < 2 kg and < 34 weeks gestation
- Infants > 12 hours at enrollment
- Severe hypotension, defined as either:
 - Mean arterial blood pressure (MAP) < gestational age in weeks, or
 - Systolic blood pressure (BP) < 45 or diastolic BP < 20
- Severe Hypertension defined as Systolic BP > 90 or diastolic > 60
- Culture-positive sepsis
- Known or strongly suspected inborn errors of metabolism
- Significant cardiac disorders, including cyanotic congenital heart disease, ductal-dependent congenital heart disease, and critical congenital heart disease (lesions requiring surgery or catheter-based intervention in the first year of life)
- Respiratory failure, defined as any requirement of positive pressure ventilation at the time of enrollment, or FiO₂ > 50%

Title: Direct Peritoneal Resuscitation in Gastroschisis

PI: [name]

Sponsor: UAMS

- Any other condition, that, in the opinion of the investigator, might interfere with the safe conduct of the study or place the subject at increased risk
- Lactic acidosis with at least one or more of the following:
 - Characterized by increased blood lactate levels ($> 5 \text{ mmol/L}$) on two occasions at least 6 hours apart
 - Severe metabolic acidosis with an arterial pH ≤ 7.0
 - Bicarbonate < 14 or $\text{CO}_2 < 12$
 - Base excess of $> -10 \text{ mEq/L}$
- Neonatal Acute Renal Failure, defined as serum creatinine $> 2.0 \text{ mg/dL}$ with anuria in the first 12 hours of life
- Neonatal Acute Hepatic Failure, defined as INR ≥ 3 [19]

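### Twenty infants per group give about 75% power on the protocol's own inputs, not the stated 80% or more

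*Combined protocol and SAP*

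**What the plan says.** The sample-size statement is in the Data Analysis section of the combined protocol and SAP. The primary outcome is time to enteral feeds of 100 kcal/kg/day. For a two-sample t-test, the section says that "a sample size of 20 in each of the two groups will yield at least 80% power to detect a 6-day difference" in the mean of that outcome, "assuming a common standard deviation of 7" and a two-sided 5% level. The paragraph before it makes two-sided 5% testing the rule for every comparison: "All tests will be two-sided assuming a significance level of 5"%.

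The Study Population section gives the matching total: "We anticipate enrolling 40 subjects at Arkansas" Children's Hospital. No other sample-size calculation, standard deviation, test or attrition allowance appears in the document.

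**The concern.** Test, group size, difference, standard deviation, level and sidedness are all printed, so the power follows from them and can be checked directly. A difference of 6 days with a standard deviation of 7 is a standardised effect of 6/7 = 0.857. For an effect of that size, 20 per group looks slightly too few for 80% power.

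This sentence is the only justification for enrolling 40 infants, and it concerns the primary outcome. If the power is overstated, the trial has a larger chance of missing the benefit it was sized to find than its readers are told. A non-significant result could then be taken as stronger evidence against a 6-day benefit than the design supports.

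**Working it through.** **Inputs, all from Data Analysis:** n = 20 per group, difference δ = 6 days, common SD σ = 7 days, two-sample t-test, two-sided α = 0.05. The total of 40 in Study Population agrees with 2 × 20.

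**Attempt to reproduce the stated power (exact, noncentral t)**

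- Standard error of the difference: σ√(2/n) = 7 × √(2/20) = 2.214 days.
- Noncentrality: δ/SE = 6/2.214 = 2.71.
- Degrees of freedom: 2 × 20 − 2 = 38. Critical value: t(0.975, 38) = 2.024.
- Power = P(|T| > 2.024), where T is noncentral t with 38 df and noncentrality 2.71. Result: **0.752**.

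A simulation of 100,000 trials agrees: 75.3% for Student's t-test and 75.2% for Welch's.

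**Normal approximation**

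Power ≈ Φ(2.71 − 1.96) = Φ(0.75) = **0.774**. This is the more favourable of the two two-sided calculations, and it also falls short of 0.80.

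**Sample size needed for 80%**

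| n per group | Total | Power, t-test | Power, normal approximation |
|---|---|---|---|
| 20 | 40 | 0.752 | 0.774 |
| 21 | 42 | 0.773 | 0.793 |
| 22 | 44 | 0.793 | 0.811 |
| 23 | 46 | 0.811 | 0.828 |

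Solving the t-test power for exactly 80% gives n = 22.37, so 23 per group. The normal formula, 2(1.960 + 0.842)² × 7²/6², gives 21.4, so 22 per group.

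**What 20 per group does deliver at 80% power (t-test)**

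- Holding SD at 7: a difference of 6.36 days.
- Holding the difference at 6: an SD of about 6.6.

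**Would a one-sided test explain the figure?**

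A one-sided 5% test gives 0.845, which would satisfy the claim. The section rules this out, because it specifies two-sided for this calculation and again for all tests.

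**Effect of losses (assumed, not document figures)**

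One infant lost per group (19 each) gives 0.729, and two lost per group (18 each) gives 0.705. The main finding does not depend on either scenario.

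**The case against.** The best defence is rounding. The difference and the standard deviation are printed as whole numbers. An SD between 6.50 and 6.59 would print as 7 and gives 80.0% to 81.2% power for 6 days. A difference between 6.37 and 6.49 would print as 6 and gives at least 80% with SD 7. So the software may have been given inputs for which the claim was true. That is possible, but nothing in the document supports it, and rounding can equally work the other way: 5.5 days with an SD of 7.49 gives about 62%. A power statement has to follow from the inputs printed beside it, and this one does not. If unrounded inputs exist, printing them would be an acceptable alternative correction.

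The second argument is that the gap is small: about 5 percentage points, 3 infants per group, or 0.36 day in detectable difference. That is true. The trial is still worth running, and no procedure, endpoint or safety rule depends on the figure. The final result would in any case be read mainly from the estimated difference and its confidence interval. This limits the harm but does not make the statement correct.

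Third, losses may be limited. The note under Eligibility Criteria allows ineligible randomised infants to be replaced, and Individual Subject Discontinuation keeps infants who stop the study fluid under scheduled assessment. Against that, Subject Withdrawal from Study ends data collection for withdrawn infants, and Safety Monitoring lists events that lead to withdrawal. Some loss is therefore possible, but the document gives no basis for its size. For that reason the attrition figures above are illustrations only.

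**Conclusion.** The concern holds. On the printed inputs, 20 infants per group give 75.2% power for a 6-day difference, and neither two-sided calculation reaches 80%. The type II error is about 25% (1 − 0.752 = 0.248) instead of at most 20%, so a true 6-day benefit would be missed about one time in four.

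The 75% figure assumes approximately normal outcomes, an SD of 7 days (for which the document gives no source) and all 40 infants analysed. It is what the protocol's inputs imply, not an independent estimate of the trial's true power. Any loss of infants would lower it.

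The shortfall is modest, but the statement is the sole basis for the sample size on the primary outcome and should be corrected.

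**What to change.** Replace the power sentence in Data Analysis with one that matches its inputs, for example: *With 20 infants per group, a two-sample t-test at the two-sided 5% level has about 75% power for a true difference of 6 days in mean time to full enteral feeds (common SD 7 days), and 80% power for a difference of about 6.4 days. These figures assume that all 40 infants are analysed.*

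If the calculation was run with unrounded inputs, print those inputs instead, with the power they give.

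The cost is one sentence and a slightly less favourable figure. The correction needs no extra infants and no change to the design or conduct. If the sponsor prefers to keep 80% power for 6 days, the same inputs require 23 per group, or 46 in total, before any allowance for loss.
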